## Synopsis

design	Prospective cohort study (population-based surveillance and serial sero-survey)
study site & population	
Polana Caniço, peri-urban Maputo, Mozambique: a health- and demographic surveillance site (HDSS) covering a population of approximately 15,393, in the catchment area of the Polana Caniço General Hospital (PCGH).
 
All individuals residing in the 2108 HDSS households for at least 3 months (infants, children, adults, elderly) are included in bi-weekly surveillance rounds, regardless of age.
 
An age-stratified random sample of that population (800 per age stratum) will be selected for the repeated sero- and social mixing survey.
 
No exclusion criteria apply for participants able and willing to provide consent for participation in the study.

duration	December 2020-December 2021 (12 months)
objectives and endpoints	
Primary objectives
 
 
Estimate the attack rate, serial interval, and reproduction number of SARS-CoV-2 infection in peri-urban Maputo.
 
Estimate the proportion of infections that are asymptomatic, and tease out the role these play in transmission.
 
Estimate the incidence rate of SARS-CoV-2 infection, COVID-19 disease (symptomatic infection), rate of severe COVID-19 disease, hospitalization for medical care and mortality, over a 12 month period in peri-urban Maputo
 
Identify risk factors for SARS-CoV-2 infection, for asymptomatic or clinical presentation, and for COVID-19-related death, which could include HIV status, nutritional status, blood group, underlying co-morbidities, household factors, pre-existing levels of anti-alphacoronavirus antibodies (CoV 229E, NL63) or anti-betacoronavirus antibodies (CoV OC43 and HKU1), and availability and adoption of measures aimed to reduce transmission.
 
Create social contact matrices that can be used to parametrize dynamic transmission models.
 
Estimate the household secondary infection rate
 
 
Secondary objectives
 
 
Measure antibody titers over time and analyze the correlation between anti-coronavirus (endemic coronavirus or SARS-CoV-2) antibody titers and reinfection
 
Assess the individual uptake of measures aimed to reduce transmission (quarantine, physical distancing, hygiene, future vaccination) and assess barriers to uptake (absence soap/water, income loss, ability to self-isolate, availability of masks, distrust, lack of understanding of the communication)
 
Derive and validate a clinical prediction rule for SARS-CoV-2 infection.
 
Geographical mapping of clusters, spread and identification of transmission hotspots
 
Sequence selected strains of SARS-CoV-2
 

	
 
Understand non-SARS-CoV-2 etiologies of respiratory disease in the study population
 
Identify factors associated with household SARS-CoV-2 infection and with household infection resulting in Covid19 disease, including viral load and symptoms of household index case, household and individual characteristics and behaviour to prevent infection.
 
Estimate total (of vaccinees) and overall (including indirect protection of non-vaccinated) vaccine effectiveness among the study population, once one or more vaccines are introduced
 

screening, recruitment & randomization	
All household members will be screened for symptoms during biweekly household visits.
 
Individuals reporting any respiratory sign, or loss of smell or taste, with or without fever (either presenting at the COVID-19 care facility or identified through the biweekly household visits) will provide specimens that will undergo PCR testing. Symptoms, clinical outcome, vaccination status against COVID-19, and potential exposure will be recorded.
 
Three age-stratified subsets of the population (0-17 years; 18-50 years; >50 years) will be recruited for a sero-survey at 0, 3, 6 and 12 months and a social mixing survey, repeated 4 times during the outbreak.
 
Household contacts of household cases testing positive for SARS-CoV-2 will be screened for virus and antibodies and for illness 1 day after confirmation of the household index case and 28 days after index case symptom onset

follow-up	
The clinical outcome of individuals with a confirmed SARS-CoV-2 infection (mild cases at home; hospitalised cases in the hospital or after discharge) will be recorded during the weekly visits and at 28 and 56 days post symptom onset.

analytical methods	
 
* Description of transmission dynamics: rolling incidence rate of COVID-19 disease throughout one year, adjusting for the sensitivity of SARS-CoV-2 RT-PCR on nasal swabs by delay between symptom onset and testing; SARS-CoV-2 infection incidence rate, SARS-CoV-2 annual attack rate, secondary infection rate, and infection fatality risk by age group, by adjusting for the proportion asymptomatics.
 
* Risk factor analysis for SARS-CoV-2 infection and COVID-19 disease, and for severity (hospitalisation), overall and following household transmission in particular.
 
* Model basic and effective reproductive numbers (<math>R_0</math> and <math>R_e</math>), generation time distribution, ratio of transmissibility between symptomatic and asymptomatic cases, duration of the infectious period, household secondary infection rate.
 
* Explore the correlation between <math>R_0</math> and <math>R_e</math>, and the uptake of measures to reduce exposure/ transmission.
 
* Case-cohort, case- control or similar analysis to estimate vaccine effectiveness against confirmed COVID-19 in the population-based surveillance and cohort analysis to estimate vaccine effectiveness against SARS-CoV-2 seroconversion (among sero-survey participants)
 

safety	
The study does not involve an investigational product or intervention

statistical methods	Descriptive (probabilistic) and inferential statistics Negative binomial regression for risk factor analysis Development of a compartmental mathematical model to describe the spread of SARS-CoV-2 on the population level
---------------------	---

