The transmission potential of SARS-CoV-2 is determined in any particular context by the basic reproduction number ( $R_0$ ) when there is no protective immunity in the population.  $R_0$  will vary with time and context, such as population density, number of contacts and environmental conditions, and is dependent on the period of infectiousness, viral load, and the serial interval. Early data estimated the  $R_0$  for SARS-CoV-2 between 2.0 and 3.4 (Ferretti 2020; Li 2020), higher than that for seasonal influenza (Biggerstaff et al 2014). This is likely in part because of key divergent features from influenza such as pre and asymptomatic SARS-CoV-2 transmission (Ferretti 2020; Kimball 2020; He 2020), near absence of severe disease in young children (Wu et al 2020), and a longer estimated serial interval of 3.96 days (Du Z Emerging Infect Dis 2020). The SARS-CoV-2 average  $R_0$  is also higher than estimated for previous novel viruses, such as influenza H1N1 in the 1918 ( $R_0=1.8$ ) and 2009 ( $R_0=1.6$ ) pandemics (Biggerstaff et al 2014) and SARS-CoV-1 ( $R_0=1-5$ ) (Liu et al 2020).

To date, evidence suggests that in temperate climates between 20 and 50% of infections could be asymptomatic (Mizumoto et al 2020; Bi et al 2020; Kimball et al 2020). Pre-symptomatic shedding is common, with comparable viral load in asymptomatic, pre-symptomatic and clinical cases (Kimball et al 2020). This complicates timely targeted application of interventions since people may not know they are infected and will not behave as if they were. The frequency of asymptomatic infection in sub-Saharan African settings is as of yet unclear, and also may vary by setting. Understanding the proportion of asymptomatic infections and their contribution to the reproduction number is important.

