Active syndromic population surveillance (biweekly) with PCR testing of symptomatic individuals – 12 months	15393 individuals (2108 households) Possible cases reporting any respiratory sign or loss of smell or taste, with or without fever, selected for PCR testing. Initially, before widespread community transmission, pooled testing of possible cases; when >50 confirmed cases per week, switch to PCR testing of 1 in 10 possible cases (systematic selection - every 10th possible case)	
 
● COVID-19 disease incidence rate (symptomatic infections per person-month)
 
● COVID-19 related hospitalisation rate
 
● Case (disease) fatality risk (%)
 
● Risk factors for severe outcome/hospitalization
 
● Basic reproduction number
 
● Effective reproduction number
 
● Serial interval
 
● Proportion uptake of measures to prevent infection; barrier uptake
 
● Effectiveness of interventions
 

		
 
• COVID-19 incidence density maps
 
• COVID-19 likelihood ratios of clinical signs
 
• Brand-specific vaccine effectiveness against confirmed COVID-19 (disease)
 

Age-stratified sero-survey at 0, 3, 6, 12 months	2400 individuals/dried blood spot samples per round (800 per age group <18yo, 18-50 yo, >50yo) An age stratified sample of individuals will be selected (simple random sample in each age group)	
 
• SARS-CoV-2 infection annual attack rate (%)
 
• Infection fatality risk
 
• Proportion asymptomatic infections, by age group
 
• Risk factors for infection
 
• Association between antibody titers and reinfection
 
• Brand-specific total vaccine effectiveness against SARS-CoV-2 seroconversion
 
• Overall vaccine effectiveness against SARS-CoV-2 seroconversion
 

Repeated social mixing survey	the same 2400 individuals selected for the sero-survey (800 per age group <18yo, 18-50 yo, >50yo)	
 
• correlation between number of contacts, intensity of contacts and attack rate
 
• correlation between uptake of control measures and attack rate
 
• social contact matrices to be used to parametrize dynamic transmission models
 

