## 4. Participants, Population & Selection

### 4.1 Setting

Polana Caniço, peri-urban Maputo, Mozambique: a health- and demographic surveillance system (HDSS) covering a population of 15,393, in the catchment area of the Polana Caniço General Hospital (PCGH), one out of two COVID-19 referral facilities in Maputo.

The population in peri-urban Polana Caniço is relatively representative of the increasingly urban population in Southern Africa, having young and mobile inhabitants. Moreover, the population suffers increasingly from non-communicable diseases, and prevalence of HIV and active tuberculosis is presumed to be important. Research gaps on COVID-19 transmission dynamics include whether the reproduction number could be different in such different (eg. younger) population. Also, the potential association between (uncontrolled) HIV infection or (active) tuberculosis and COVID-19 infection and severe disease, needs to be elucidated.

The Polana Caniço-HDSS has been established since 2017. In total, as of time of writing, 2108 households (defined as residents of the same building, sharing a cooking area) have been enrolled in the HDSS. All members residing in the household for at least 3 months (infants, children, adults, elderly) are enrolled in the HDSS. Surveillance rounds are currently carried out six-monthly. Demographic and health indicators collected in each surveillance round include but are not limited to: fertility/birth rate, mortality/cause of death, migration, disease cases, trauma and violence, socioeconomic status, water and sanitation facilities, risk factors for the acquisition of chronic diseases, women's health and family planning, immunization, risk behaviours and cultural practices related to the transmission of STI (including HIV and syphilis). Testing for HIV and syphilis is planned to be added as part of the surveillance rounds, from October 2020 onwards. Data on births, deaths, internal and external migration, pregnancies and their outcomes, and any other relevant events from a demographic perspective, are continuously reported by community key informants and confirmed through home visits.

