## 7. Statistical Analyses

### 7.1 Methods

All estimated transmission or clinical outcome indicators will be adjusted for the design effect, related to the selection of HDSS enumeration areas (clusters) within the source populations. Intraclass correlation coefficients can be deducted from previous studies in the HDSS. The results of the sero-survey and social mixing survey will additionally be adjusted for age-stratified sampling.

We will calculate a incidence rate of COVID-19 disease throughout one year, adjusting for the sensitivity of SARS-CoV-2 RT-PCR on nasal swabs by delay between symptom onset and testing. Using the longitudinal sero-survey data, determining the proportion of asymptomatics, we will be able to adjust the clinical incidence rate to a SARS-CoV-2 infection incidence rate, and determine the SARS-CoV-2 infection annual attack rate and the infection fatality risk by age group.

We will undertake three risk factor analyses: of SARS-CoV-2 infection, of COVID-19 disease (symptomatic infection), and of COVID-19 hospitalisation and death (severe disease). Using negative binomial regression, we will investigate the association with socio-demographic factors, clinical characteristics such as underlying medical conditions, and uptake of preventive measures. We also investigate the association between SARS-CoV-2 infection (from the sero-survey) and recent exposure, contact and mobility patterns (from the social mixing questionnaire).

We will assume everyone will be susceptible initially and basic and effective reproductive numbers ( $R_0$  and  $R_e$ ) will be calculated by the rate of change of incidence over successive serial intervals (time between onset of infection of index and onset of infection of infected).

We will use established methods (Cauchemez et al 2004; te Beest et al 2013) to estimate generation time distribution, ratio of transmissibility between symptomatic and asymptomatic cases, duration of

the infectious period, and the basic reproduction number, from the transmission data collected in households.

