## 7.2 Sample size and power

Assuming a 40% annual attack rate, 50% symptomatic infections (cases), 2% overall case fatality risk, of which 90% are identified by the active population surveillance, 2790 COVID-19 cases and 56 deaths will be identified through the study period. The average incidence rate of the HDSS population would then be 1.50 cases per 100 person months with lower and upper 95% confidence interval limits 1.45 and 1.56. The overall case fatality risk would have as lower and upper 95% confidence interval limits at 1.53 and 2.58%.

To determine the infection attack rate from a simple random population sample of three age strata (comparable in size), with +/-3% confidence limits, 95% confidence interval, assuming the attack rate may reach 40% towards the end of the study period, samples from 800 individuals per age stratum per round will need to be collected.

Assuming the household secondary attack rate to be close to 17% (Fung et al, Clin Infect Dis, 2020) and a median household size of 7.3 (based on HDSS data), a 5% confidence limit and a design effect of 3, 642 household members will need to be enrolled, or 100 households. The WHO also recommended to include 100 households in household transmission investigations.

Assuming 20% vaccination coverage among the 2400 sero-survey participants, 5% of sero-conversion over 3 months and 10% of seroconversion over 6 months, a 95% two-sided confidence interval and an anticipated crude total vaccine effectiveness of 50%, there will be 66% power to observe this effect after 3 months and 97% power after 6 months.

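### The planned correlation of Re with uptake of control measures does not allow for accumulating immunity, so a measure with no effect can appear to work, or to harm, if its uptake trends over the year

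*Combined protocol and SAP*

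**What the plan says.** The Synopsis, under analytical methods, will explore the correlation between R0 and Re "and the uptake of measures to reduce exposure/ transmission". Section 7.1 explains how the two numbers are obtained: "We will assume everyone will be susceptible initially and basic and effective reproductive numbers" "will be calculated by the rate of change of incidence over successive serial intervals". It gives no susceptible share for later time points.

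Table 1 (Section 2) lists "Effectiveness of interventions" among the surveillance outcomes. It is not in bold, so it is not a primary outcome measure. Section 1.1 defines R0 as applying "when there is no protective immunity in the population", and adds that it varies with time and context. The Synopsis counts vaccination, once available, among the measures whose uptake is assessed.

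Uptake is updated at every household visit (Section 3). It is also asked in four social mixing rounds, whose timing depends on the stage of the outbreak (Section 5.1). Serology is planned at 0, 3, 6 and 12 months.

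**The concern.** Re taken from incidence growth is the product of two things: transmissibility, which control measures may change, and the susceptible share, which shrinks as people are infected. Over a year with substantial infection, Re falls even if nobody changes behaviour. Any series that drifts in one direction over the same year will then be correlated with it. Rising uptake makes a useless measure look protective, and waning uptake makes it look harmful.

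Such a drift is plausible here. Cumulative vaccination can only rise, and it also lowers susceptibility. The social mixing rounds follow the epidemic phase: one while cases rise, one after an initial peak.

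What is at stake is interpretation. Section 1.2 aims to assess the impact of behavioural interventions on transmissibility. Section 10.2 reports the evolution of the reproduction number to health authorities and the national response team after 3, 6 and 12 months. Depletion of susceptibles could be read there as an effect of measures.

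**Working it through.** **Inputs from the documents.** Section 7.2: "Assuming a 40% annual attack rate, 50% symptomatic infections (cases), 2% overall case fatality risk", "of which 90% are identified by the active population surveillance". Section 4.1: an HDSS "covering a population of 15,393". Box in Section 1.2: 3.8% seroprevalence in Maputo city in August 2020. Section 1.1: serial interval 3.96 days.

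**Step 1. Reproduce the plan's figure.** Cases = 15,393 × 0.40 × 0.50 × 0.90 = 2,771, against 2,790 stated (0.7% lower; 15,500 people would give exactly 2,790). Deaths at 2% are 55 to 56, against 56 stated. The rate is 0.40 × 0.50 × 0.90 / 12 = 1.50 per 100 person-months, as stated. The 40% attack rate is therefore the plan's working scenario.

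**Step 2. Mechanical fall in Re.** With constant transmissibility, Re(t) = R0 × S(t).

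- With 3.8% prior immunity, S goes from 1 - 0.038 = 0.962 to 0.962 - 0.40 = 0.562. The ratio is 0.562 / 0.962 = 0.584, a fall of about 42%.
- With no prior immunity, S goes from 1.00 to 0.60, a fall of 40%.
- A deterministic SIR model solved for a 40% attack rate in a year needs R0 of about 1.34. Re then runs from 1.34 × 0.962 = 1.29 to 1.34 × 0.562 = 0.75.

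**Step 3. Correlation with a measure that does nothing.** Pearson r is taken over 26 fortnightly points. The following are assumptions, not in the documents: the SIR form, 5 to 20 initial infections, the 7-day upper value for the serial interval or infectious period, the uptake paths, and the 10% and 20% attack rates. The noise-free row uses uptake rising from 30% to 60%. The other rows use uptake between 30% and 70% with noise of SD 5 percentage points, and 10% error in Re. They show medians over simulated runs.

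| Uptake of the null measure | Attack rate | Error in Re | r |
|---|---|---|---|
| Linear rise | 40% | none | -0.75 to -0.94 |
| Linear rise | 40% | 10% | -0.61 to -0.76 |
| Linear fall | 40% | 10% | +0.61 to +0.76 |
| Step up at day 120 | 40% | 10% | -0.64 to -0.83 |
| Tracks incidence | 40% | 10% | +0.37 to +0.48 |
| Mid-year hump | 40% | 10% | -0.36 to -0.49 |
| Flat | 40% | 10% | 0.00 |
| Linear trend | 20% | 10% | 0.54 to 0.61 in size |
| Linear trend | 10% | 10% | 0.30 to 0.34 in size |

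The values at a 10% attack rate are weak because the fall in Re (0.10 / 0.962 = about 10%) is then no larger than the assumed error.

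**Step 4. Divide by the susceptible share.** Using Re(t)/S(t), the median r for the null measure is about 0 in every scenario, with a 95% range of about -0.4 to +0.4. With a linear trend at a 40% attack rate, |r| exceeds 0.39 (roughly the two-sided 5% point for 26 observations) in at least 99% of runs before the division. After it, the share is 4% to 6%. This step uses the model's own S(t), so it shows the best case. An S(t) interpolated from four survey rounds will do less well.

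**The case against.** The strongest reply is that this is one exploratory line in the Synopsis, feeding a secondary outcome, and that the plan has other ways to relate measures to infection. That is correct. Section 7.1 plans negative binomial regressions of infection, disease and severe disease on uptake of preventive measures. Table 1 lists a separate correlation of uptake with attack rate. Section 7.1 also has a compartmental model, fitted or validated with sero-survey attack rates, which can carry depletion, and separate vaccine effectiveness designs. A reader might infer that the Re correlation is the only basis for judging interventions; the documents do not support that. However, none of these routes is linked to the correlation, and the model is described as projecting intervention scenarios, not as estimating the effect of observed uptake.

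A reader might also infer that any ineffective measure will show a strong correlation. It will not: the result depends on uptake trending, on the attack rate and on the noise in Re. The 40% is a planning value, and the calibrated R0 of 1.34 is below the 2.0 to 3.4 quoted in Section 1.1. The plan does not give the unit of correlation, which might be spatial and not temporal. Variants or seasonality would mean that Re(t)/S(t) is not constant even for a null measure.

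Finally, a reader might conclude that R0 is a single number and has no place in the analysis. Section 1.1 says otherwise: R0 varies with context and is defined without immunity, so as defined it is free of this artefact. What stands is narrower. Section 7.1 gives R0 and Re one growth-based calculation and does not say how they are separated once immunity has built up.

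**Conclusion.** The point holds in conditional form. The stated correlation leaves the susceptible share inside Re, and no section adjusts this analysis for it. Under the plan's own attack rate, Re falls by 40% to 42% with transmissibility unchanged, and a zero-effect measure can then show a strong correlation in either direction if its uptake trends over the year. The fall in Re rests on the plan's 40%, the August 2020 seroprevalence and constant transmissibility. The correlations also rest on the assumed SIR form, uptake paths and error in Re.

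The weight is modest. The analysis is exploratory and no primary outcome measure depends on it. The remedy uses data already being collected, so it is worth making.

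**What to change.** In Section 7.1 and the Synopsis, replace the correlation with one of the following, for non-vaccine measures only:

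- A regression of log(Re(t)/S(t)) on uptake in the preceding period. S(t) is the age-weighted susceptible share interpolated from the sero-survey rounds, errors are autocorrelated, and the uncertainty in S(t) is carried into the interval.
- Estimation of the uptake effect inside the transmission model of Section 7.1.

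State the unit and number of points analysed, and label the result exploratory and ecological.

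Keep vaccination out of this regression as an exposure. Dividing by a susceptible share that reflects vaccination removes the pathway through which vaccination acts and would bias its effect toward zero. Assess it with the case-cohort and cohort designs in Section 7.1.

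If R0 is kept, state that it means the immunity-free quantity of Section 1.1, and not growth-based Re from later in the year.

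The cost is analysis-plan wording and no new data collection. Intervals will widen, by an amount not computed here, most of all between months 6 and 12, where no sero-survey round falls. Possible antibody waning (Section 1.1) adds to the uncertainty in S(t).
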